#### 8.4.4 Weeks 1-6

- Record vital signs (Pre & Post)
- Review concomitant medications and treatments
- Collect adverse events
- During the treatment phase, administer treatments 5 days per week but at a minimum 3 days per week up to a maximum of 35 treatments total. (All treatment subjects will have an initial four treatments (which are part of the planned 35 treatments) in which the PSI will be gradually increased to maximum tolerability with the goal of reaching 3-6 PSI by the fifth treatment).

---

8.4.5 Week 6 – Day 42 (+/- 2 days)

- Cognitive assessments: It is recommended that subjects come in the day following treatment for all assessment testing but no later than 2 days (48 hours) post last treatment. Administer cognitive assessments including:
  - vADAS-Cog (must be administered first and before 3:00 PM; should be administered at the same time of day)
  - ADCS-CGIC
  - ADCS-ADL
  - Trail Making A & B
- Record vital signs (If non-treatment day)
- TUG Test
- Functional Reach Test
- NPI
- Exercise regimen
- Patient Questionnaire
- Review concomitant medications and treatments,
- Collect adverse events
- If treatment occurs on same day as assessments complete the treatment first
  - Vitals (Pre & Post)
  - During the treatment phase, administer treatments 5 days per week but at a minimum 3 days per week up to a maximum of 35 treatments total

8.4.6 Weeks 7-12

- Record vital signs (Pre & Post)
- Review concomitant medications and treatments
- Collect adverse events
- During the treatment phase, administer treatments 5 days per week but at a minimum 3 days per week up to a maximum of 35 treatments total (or during maintenance, administer two treatments per week separated by at least 2 days up to 24 weeks)

8.4.7 Week 12 – Day 84 (+/- 2 days)

- Cognitive assessments: It is recommended that subjects come in the day following treatment for all assessment testing but no later than 2 days (48 hours) post last treatment. Administer cognitive assessments including:
  - vADAS-Cog (must be administered first and before 3:00 PM; should be administered at the same time of day)
  - ADCS-CGIC
  - ADCS-ADL

---

Confidentiality Statement

---

The confidential information in this document is provided to you as an investigator or consultant for review by you, your staff, and the applicable Institutional Review Board. Your acceptance of this document constitutes agreement that you will not disclose the information contained herein to others without written authorization from the sponsor.

- Trail Making A & B
- Record vital signs (If non-treatment day)
- TUG Test
- Functional Reach Test
- Health Resource Utilization Survey - RUI
- NPI
- Exercise regimen
- Patient Questionnaire
- Review concomitant medications and treatments,
- Collect adverse events
- If treatment occurs on same day as assessments administer treatment first
  - Vitals (Pre & Post)
  - During the treatment phase, administer treatments 5 days per week but at a minimum 3 days per week up to a maximum of 35 treatments total (or during maintenance, administer two treatments per week separated by at least 2 days up to 24 weeks)
- Draw blood for:
  - Blood lipid panel, CBC, fibrinogen, CRP, LP-PLA2, MPO, lipoprotein particles to include: LDL-P, Lp(a)-P, VLDL-P, IDL-P, ApoB, B12, TSH
  - Blood viscosity

#### 8.4.8 Weeks 13-18

- Record vital signs (Pre & Post)
- Review concomitant medications and treatments
- Collect adverse events
- Administer two treatments per week separated by at least 2 days as maintenance up to 24 weeks

#### 8.4.9 Week 18 – Day 126 (+/- 2 days)

- Cognitive assessments: It is recommended that subjects come in the day following treatment for all assessment testing but no later than 2 days (48 hours) post last treatment. Administer cognitive assessments including:
  - vADAS-Cog (must be administered first and before 3:00 PM; should be administered at the same time of day)
  - ADCS-CGIC
  - ADCS-ADL
  - Trail Making A & B
- Record vital signs (If non-treatment day)
- TUG Test

---

#### Confidentiality Statement

---

The confidential information in this document is provided to you as an investigator or consultant for review by you, your staff, and the applicable Institutional Review Board. Your acceptance of this document constitutes agreement that you will not disclose the information contained herein to others without written authorization from the sponsor.

- Functional Reach Test
- NPI
- Exercise regimen
- Patient Questionnaire
- Review concomitant medications and treatments
- Collect adverse events
- If treatment occurs on same day as assessments administer the treatment first
  - Vitals (Pre & Post)
  - Administer two treatments per week separated by at least 2 days as maintenance up to 24 weeks

8.4.10 Weeks 19-24

- Record vital signs (Pre & Post)
- Review concomitant medications and treatments
- Collect adverse events
- Administer two treatments per week separated by at least 2 days as maintenance up to 24 weeks

8.4.11 Week 24 – Day 168 (+/- 2 days)

- Cognitive assessments: It is recommended that subjects come in the day following treatment for all assessment testing but no later than 2 days (48 hours) post last treatment. Administer cognitive assessments including:
  - vADAS-Cog (must be administered first and before 3:00 PM; should be administered at the same time of day)
  - ADCS-CGIC
  - ADCS-ADL
  - Trail Making A & B
  - Logical Memory I & II
- MOCA
- Vital signs (If non-treatment day)
- Hachinski
- MMSE2
- TUG Test
- Functional Reach Test
- Health Resource Utilization Survey - RUI
- NPI
- Exercise regimen
- Patient questionnaire

---

Confidentiality Statement

---

The confidential information in this document is provided to you as an investigator or consultant for review by you, your staff, and the applicable Institutional Review Board. Your acceptance of this document constitutes agreement that you will not disclose the information contained herein to others without written authorization from the sponsor.

- Review concomitant medications and treatments
- Collect adverse events
- If treatment occurs on same day as assessments administer the treatment first
  - Vitals (Pre & Post)
  - Administer two treatments per week separated by at least 2 days as maintenance up to 24 weeks
- Draw blood for:
  - Blood lipid panel, CBC, fibrinogen, CRP, LP-PLA2, MPO, lipoprotein particles to include: LDL-P, Lp(a)-P, VLDL-P, IDL-P, ApoB, B12, TSH
  - Blood viscosity
- MRI (Must be done after last treatment but may take place on or before the Week 24 Assessment Visit)

For sites collecting data for exploratory endpoints, complete the following assessments:

- Ultrasound: Transcranial Doppler; cerebral artery blood flow
- Moor deep tissue oxygenation

#### 8.4.12 Month 9 (Week 36) – Day 252 (+/- 7 days)

- Administer cognitive assessments including:
  - vADAS-Cog (must be administered first and before 3:00 PM; should be administered at the same time of day)
  - ADCS-CGIC
  - ADCS-ADL
  - Trail Making A & B
  - Logical Memory I & II
- MOCA
- Record vital signs
- TUG Test
- Hachinski
- Functional Reach Test
- Health Resource Utilization Survey-RUI
- NPI
- Exercise regimen
- Patient Questionnaire
- Medical History, if not collected at screening visit
- Review concomitant medications and treatments
- Collect adverse events

---

8.4.13 Month 12/Study Termination – Day 365 (+/- 7 days)

- Administer cognitive assessments including:
  - vADAS-Cog (must be administered first and before 3:00 PM; should be administered at the same time of day)
  - ADCS-CGIC
  - ADCS-ADL
  - Trail Making A & B
  - Logical Memory I & II
- MOCA
- Vital signs
- Physical Exam including neuro
- Hachinski
- TUG Test
- Functional Reach Test
- Health Resource Utilization Survey - RUI
- NPI
- Exercise regimen
- Patient Questionnaire
- Patient Satisfaction Survey
- MMSE2
- Review concomitant meds and treatments
- Collect adverse events
- Draw blood for:
  - Blood lipid panel, CBC, fibrinogen, CRP, LP-PLA2, MPO, lipoprotein particles to include: LDL-P, Lp(a)-P, VLDL-P, IDL-P, ApoB, B12, TSH
  - Blood viscosity
- MRI (Must be completed within 14 Days prior to the Month 12 Visit)
- Complete Study Disposition Form

8.4.14 Early Termination Visit

All procedures scheduled for the 12 month/final visit should be performed in the event of an early termination visit. The subject should be encouraged to complete these assessments.

8.4.15 Study Disposition

Subjects will be discharged from the study to their pre-study routine. Ideally, subjects will continue in the study to complete the assessments and the 12 month visit. All subjects in the active sham arm will be eligible to participate in an active treatment follow up study after completion of the 12 month visit.

---

Confidentiality Statement

---

The confidential information in this document is provided to you as an investigator or consultant for review by you, your staff, and the applicable Institutional Review Board. Your acceptance of this document constitutes agreement that you will not disclose the information contained herein to others without written authorization from the sponsor.

## 8.5 ONGOING ASSESSMENTS

### 8.5.1 Concomitant Medications, Treatments and Exercise

Subjects will be expected to be on stable medication for 30 days prior to study start and through the first 24 weeks of the study for chronic conditions. Changes in concomitant medications will be recorded. Treatment for adverse events will be recorded. The current use of medication that in the investigator’s judgement are incompatible with study goals will be prohibited and may result in the subject’s withdrawal from the study. Subjects should not begin any other treatments that, in the investigator’s judgement may affect cerebral blood flow.

Subjects will be requested to maintain their pre study exercise regimen throughout the first 24 weeks of the study. Exercise level will be assessed at baseline, 6, 12, 18, and 24 weeks, 9 months and 12 months.

### 8.5.2 Laboratory Evaluations

Laboratory evaluations will occur at all the time points specified in the time and events schedule. The laboratory evaluations that will be performed are listed in **Figure 2**.

Blood Chemistry		
Sodium	Potassium	Blood urea nitrogen
AST	Glucose	Total bilirubin
ALT	Creatinine	Albumin
Total cholesterol	Serum calcium	Globulin
Triglycerides	Chloride	B12
Total protein	Bicarbonate	TSH
Hematology		
Hemoglobin	White blood cell count total and differential	
Hematocrit	Red blood cell count	
Platelets		
Exploratory Labs		
ApoE	CRP	Blood viscosity
Fibrinogen	LP-PLA2	
Lipid panel	MPOS	

Figure 2: Laboratory evaluations to be performed

Abnormal laboratory test results of a magnitude deemed clinically significant by the investigator will be repeated as soon as possible (preferably within 48 hours) to rule out laboratory error. For tests where there is a persistent abnormality, repeat analyses shall be performed until the cause is determined and return to baseline occurs or the investigator deems the abnormality to be of no clinical significance. If these values are deemed clinically significant then these tests should be discussed with the medical monitor. If these abnormalities are accompanied by clinical symptoms, then these should be captured as AEs.

---

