### 6.4 Withdrawal or Termination

After randomization, all treatment subjects will have an initial four treatments (which are part of the planned 35 treatments) in which the PSI will be gradually increased to maximum tolerability with the goal of reaching 3-6 PSI by the fifth treatment. Subjects are not to be terminated if they cannot reach 3-6 PSI. Each treatment session will last for 60-minutes and a treatment session 30 minutes or more ( $\geq 30$  minutes) will be considered as a completed session.

The investigator can decide to withdraw a subject if any clinical adverse event, laboratory abnormality, or other medical condition or situation occurs such that continued participation in the study would not be in the best interest of the subject. Further, if a subject meets an exclusion criterion that precludes further study participation, she/he will be withdrawn from the study.

---

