### 9.1 Adverse Events

An adverse event (AE) is any untoward medical occurrence experienced by a subject in conjunction with their participation in a clinical trial regardless of whether the event is related to the procedure or study device. An AE can be any unfavorable and unintended sign, symptom, or disease temporally associated with the use of an investigational device whether or not it is related to the investigational device. This includes any condition that is new in onset (not present prior to study treatment) or aggravated in severity or frequency from the baseline condition, any condition resulting from concurrent illness,

---

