#### Confidentiality Statement

---

The confidential information in this document is provided to you as an investigator or consultant for review by you, your staff, and the applicable Institutional Review Board. Your acceptance of this document constitutes agreement that you will not disclose the information contained herein to others without written authorization from the sponsor.

reactions to concomitant medications, progression of disease states, and also includes abnormal lab test results if associated with clinical signs or symptoms judged by the investigator to be clinically significant.

All AEs that occur after the consent form is signed must be reported in the AE section of the CRF. Documentation for all AEs should contain the Adverse Event (medical condition), the date the AE started and if applicable, the stop date; the preliminary assessment of the relationship to study treatment; any action taken with regard to study treatment; the outcome of the event; whether the event was serious and if so, whether the event was anticipated or unanticipated; and whether treatment was required.

For purposes of this study, a Serious Adverse Event (SAE) is defined in accordance with ISO 14155-2011(en), Clinical Investigation of Medical Devices, as an adverse event that, in the view of the Investigator or the sponsor:

- Led to death
- Led to serious deterioration in the health of the subject that resulted in:
  - i. Inpatient hospitalization or prolong hospitalizations
  - ii. Life threatening illness or injury
  - iii. Permanent impairment of a body structure or a body function
  - iv. Medical/Surgical intervention to prevent one of the outcomes listed in line ii. or iii. above

The sponsor is using the above ISO-14155-2011(en) definition of a SAE as an extra safety precaution in this study since no definition of “serious adverse effect” exists in Federal regulations governing medical device clinical trials, 21 CFR Part 812, Investigational Device Exemptions.

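### Section 8.5.2 ties AE recording of a confirmed, clinically significant laboratory abnormality to symptoms, so a symptom-free one that leads to intervention or withdrawal need not be recorded as an AE or assessed as an SAE

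*Protocol*

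**What the plan says.** Four places in the protocol bear on whether a laboratory abnormality becomes an adverse event.

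- **Section 8.5.2, Laboratory Evaluations.** A result that the investigator finds clinically significant is repeated to rule out laboratory error, and a persistent one is followed. Then: "If these values are deemed clinically significant then these tests should be discussed with the medical monitor". The next sentence is the only recording instruction: "If these abnormalities are accompanied by clinical symptoms, then these should be captured as AEs".
- **Section 9.1, general AE definition.** An AE is "any untoward medical occurrence experienced by a subject in conjunction with their participation in a clinical trial", whether or not it is related to the device. New or worsened conditions are included.
- **Section 9.1, laboratory clause and SAE definition.** The AE definition "also includes abnormal lab test results if associated with clinical signs or symptoms judged by the investigator to be clinically significant". An SAE is then defined "as an adverse event that, in the view of the Investigator or the sponsor", led to death or to one of several forms of serious deterioration. One of these is "Medical/Surgical intervention to prevent one of the outcomes listed in line ii. or iii. above".
- **Section 6.4, Withdrawal or Termination.** "The investigator can decide to withdraw a subject if any clinical adverse event, laboratory abnormality" or another medical condition makes continuing contrary to the subject's interest. The laboratory abnormality is listed beside the clinical adverse event, not as an example of one.

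Section 5.2.2 counts adverse events, laboratory results and vital signs as the safety measures. Section 9.3.2 requires SAEs to be reported in writing within 3 working days of the site becoming aware.

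**The concern.** An abnormality that has been repeated, has persisted and has been judged clinically significant has already passed the tests that matter for a safety record. Making the record depend further on symptoms selects on how the subject feels, and important laboratory changes can be silent.

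The AE record is where section 9.1 asks for the relationship to treatment, the action taken, the outcome and the seriousness. Section 8.5.2 asks for none of these for a laboratory value that stops short of being an AE. If such a value leads to intervention or withdrawal, the AE and SAE comparison between arms can understate harm, and an AE-based listing of reasons for withdrawal can omit it.

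Section 9.4 adds to this: the principal investigator is not blinded. Deciding whether a mild complaint accompanies an abnormal value is therefore a subjective step taken by someone who knows the arm.

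**Working it through.** No alpha, power, sample size or rate is involved, so there is no figure to reproduce. The check sets the passages side by side.

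**Step 1. What triggers an AE record.** Take an abnormality that is confirmed on repeat and clinically significant, and vary only what accompanies it.

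| Accompanied by | 8.5.2 | 9.1, laboratory clause | 9.1, general definition |
|---|---|---|---|
| Symptoms | Record as AE | Included | Included |
| An objective sign, no symptom | No instruction to record | Included | Included |
| Neither | No instruction to record | Not included by this clause | Could be included, if the site regards it as an untoward occurrence or a new condition |

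The second row shows that 8.5.2 and 9.1 do not match: one says symptoms, the other signs or symptoms. The third row shows that the answer depends on which paragraph a site follows.

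**Step 2. Whether intervention or withdrawal changes the answer.** It does not in 8.5.2, where neither is named as a trigger. It does not in the laboratory clause of 9.1 either. In 6.4 a laboratory abnormality can end participation, but nothing there says that it must then be recorded as an AE.

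**Step 3. What follows for SAEs.** The SAE definition in 9.1 begins from an adverse event. Intervention to prevent a serious outcome is a seriousness criterion, but it is applied to something already classed as an AE. If a site following 8.5.2 makes no AE record, nothing prompts it to apply the criterion, and the 3-working-day clock in 9.3.2 is not started.

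**Step 4. What is still captured.** The value itself stays in the laboratory data, which sections 5.2.2 and 9 treat as a safety measure. A clinically significant value goes to the medical monitor. Changes in concomitant medication are recorded under 8.5.1. After withdrawal, 6.4 starts safety follow-up for adverse events, and 8.4.14 asks for the month-12 procedures, which include AE collection, blood draws and the disposition form.

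**Step 5. Size.** Table 2 schedules laboratory draws at three points after screening: week 12, week 24 and month 12. The documents give no frequency for clinically significant, symptom-free abnormalities, and none for the smaller group leading to intervention or withdrawal. Even the opportunity to detect them is unclear: section 8.2 says the metabolic panel is repeated during the study, but the draw lists in 8.4.7, 8.4.11 and 8.4.13 do not name it. No count of affected subjects can be derived.

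**The case against.** The strongest reply is that nothing in the protocol forbids the record. The general definition in 9.1 is broad, its laboratory clause adds to that definition and does not restrict it, and 8.5.2 says that abnormalities with symptoms are AEs without saying that others are not. An investigator facing an abnormality serious enough to need preventive intervention could properly call it an untoward occurrence and then an SAE.

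This stands, and it limits the point. A reader might infer that a symptom-free abnormality is excluded from AE status and can never become an SAE; the text does not support that. What survives is that 8.5.2, the section a site would consult for a laboratory result, does not require the record, while another paragraph permits it.

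A reader might also infer that withdrawals for laboratory reasons go untracked. They do not: the follow-up in 6.4, the early termination visit in 8.4.14 and the medical-monitor step in 8.5.2 all remain. None of these, however, states that the abnormality itself is to be recorded as an AE. The Manual of Procedures and the CRF guidelines cited in 9.2 and 9.5 are not available and may say more, but they would be supplementing protocol wording that should be consistent in itself.

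The device risks listed in section 3.1 are not laboratory toxicities, and the study has nonsignificant-risk status. That lowers the expected number of cases. It does not resolve the inconsistency in a trial described as pivotal, with safety among its objectives.

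Finally, clarifying the rule does not cure assessor bias. Clinical significance would still be judged by an unblinded investigator; only the additional judgement about symptoms would go.

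**Conclusion.** The point holds as a defect in a stated recording rule. Followed as written, 8.5.2 requires no AE record, and so prompts no SAE assessment or expedited report, for a confirmed, clinically significant, symptom-free laboratory abnormality, even one that leads to intervention or withdrawal. Because the general definition in 9.1 would let another site record the same event, capture can be both incomplete and uneven across the up to 16 sites foreseen in section 6.3.

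The effect is confined to AE and SAE counts, their attribution, expedited reporting and AE-based withdrawal listings. The laboratory values are not lost, and the efficacy analysis is untouched. The number of subjects affected is unknown and may be small. The conclusion rests on the wording of 6.4, 8.5.2 and 9.1 alone and assumes that at least some sites will take 8.5.2 literally. It should be corrected, but it does not invalidate the trial.

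**What to change.** Reconcile sections 6.4, 8.5.2 and 9.1. State in both 8.5.2 and 9.1 that a laboratory abnormality is recorded as an AE, with or without signs or symptoms, if either:

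- it is confirmed on repeat and judged clinically significant; or
- it leads to intervention, interrupted sessions or withdrawal.

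Add that each such AE is assessed against the SAE criteria in 9.1 and, where it meets them, reported under 9.3.2. Use the same wording in both sections so that the difference between symptoms and signs or symptoms disappears. In 6.4, a cross-reference is enough to make clear that a laboratory abnormality leading to withdrawal has an AE record.

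This changes recording only. It leaves open when a subject should be treated, interrupted or withdrawn. The cost is a few sentences, a few more AE entries and a slightly higher reported AE rate in both arms.
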